relapses occur within the first few weeks of abstinence[19], this can be improved by recruiting quitters who have just quit, and starting the WhatsApp groups as soon as possible. Second, the intervention content and dosage through social media needs to be revised to increase participation. For instance, only 6 out of the 16 participants, who reported relapse at 2-month, shared their relapse experience in the group. The few number of reports of relapse posed barriers for early intervention. Due to limited number of eligible participants, some groups had only 2 to 5 participants, which led to inactive discussion. About one-fourth of the participants only stayed in the group, but did not post anything. These findings highlighted the importance of skilful and theory-driven group moderation, and inclusion of more updated and interesting content to increase the level of participation. Lastly, for a larger RCT, we shall add more recruitment sites to increase participant recruitment and generalizability. A subsequent cost-effectiveness analysis based on trial data will establish the optimal balance between costs and health effectiveness outcomes, and provide health economic data to policymakers to facilitate informed decision-making of health interventions for tobacco control

c) Aims and Hypotheses to be Tested:

This study aims to examine the effectiveness and cost-effectiveness of WhatsApp group discussion for smoking relapse prevention. To assess the effect due to treatment modality through the WhatsApp social group, we will analyse the frequency and topics of the posts in each social group and in each participant. The primary hypothesis is whether quitters who participate in the WhatsApp group discussion will have a higher prevalence of validated tobacco abstinence at 12-month follow-up than those who do not. Our second hypothesis is that greater participation in the social groups, indicated by number of posts received, posted and/or viewed, was associated with higher likelihood to quit at 12-month. The third hypothesis is that the WhatsApp intervention for a recent quitter is a more cost-effective option for tobacco abstinence and prolonged survival when compared to the control group.

d) Plan of Investigation:

(i) Subjects

Inclusion criteria:

- Smoke at least 1 cigarette per day at the service intake
- Aged 18 years or above
- Have enrolled or re-enrolled in the smoking cessation treatment for no more than 8 weeks
- No smoking for 7 to 14 days

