The primary outcome is biochemically validated (exhaled carbon monoxide < 4ppm; or/and saliva cotinine < 10ng/ml) tobacco abstinence at 12-month follow-up, which have been confirmed as a stringent criterion for abstinence verification for quitters who use nicotine replacement therapy^[21]. Secondary outcomes include prevalence of self-reported 7-day and continuous abstinence over the study period, and relapse rate, which is defined as the proportion of quitters who smoke at least 5 cigarettes in 3 consecutive days over the study period. Ancillary outcomes include change in frequency and intensity of smoking urge, change in the Minnesota Nicotine Withdrawal Scale (MNWS), and the change in HRQOL measured by Short-form 6-item instrument and EuroQoL 5-dimension 5-level (EQ-5D-5L) health utility scores from baseline to follow-ups. For cost-effectiveness analysis, the outcomes are the incremental cost-effectiveness ratio (ICER) in terms of cost per an additional tobacco abstinence gained for intervention compared to control group, and the ICER in terms of cost per life-years gain or quality-adjusted life-years gained for intervention versus control group.

(iii) Study design A pragmatic open-labelled 2-arm randomized controlled trial

(iv) Data processing and analysis

Statistical analysis

By intention-to-treat analysis (in line with CONSORT guideline), participants who are lost or refuse the follow-up will be treated as smokers with no changes in daily cigarette consumption. The analysis with multiple imputation (MI) procedure to impute the missing exhaled CO will be conducted as sensitivity analysis. Considering the correlated outcomes of participants within the same WhatsApp group, a post-hoc analysis by generalized estimating equation (GEE) model will be used to summarise the intervention effect with the odds ratios, with and without adjustment for baseline characteristics. Number needed to treat (NNT), which shows the number of treated subjects needed to have one additional quitter at 12-month, will be computed by taking the reciprocal of the risk difference between the 2 RCT groups. Number of posts received, posted or/and viewed in each participant and in each social group will be documented, and then included in the final GEE model to assess their association with the cessation outcome.

Text mining of the WhatsApp groups

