Cost-effectiveness analysis will be undertaken to indicate whether the intervention will be more cost-effective or even cost-saving option for a quitter over a time horizon of one year (within trial period) and lifetime. Within and lifetime cost-effectiveness analyses will be populated based on the healthcare provider perspective.

Model parameters input will be identified through within trial data and a review of local and overseas literature, where necessary. Within trial cost-effectiveness of WhatsApp intervention versus control group will be evaluated using total costs, the number of tobacco abstinence and total QALYs over the study period. EQ-5D-5L utility data at baseline and follow-ups from trial will estimate QALYs in two groups using area under the curve technique. Lifetime cost-effectiveness will be performed via Markov modelling that will simulate the annual health status progression of subjects in either intervention or control group (Appendix 8). Both the successful and unsuccessful quitters after the trial will be subject to the annual transition probability from a status of no diseases to lung cancer, cardiovascular diseases, and other diseases, and then mortality. Former smokers may be relapsed after abstinence. Discounting will only be applied to total costs and QALY calculation under the lifetime horizon. Sensitivity analyses will be conducted where each parameter will be set at plausible lower and upper bounds based on 95% confidence interval of estimates in above data analysis.

The incremental cost-effectiveness ratio (ICER) in terms of cost per an additional tobacco abstinence gained, life-years gained, or QALYs gained for the intervention group in comparison to the control group will be reported. The WhatsApp intervention will be considered as cost-

effective if its ICER will be less than 3 times per capita gross domestic product in Hong Kong recommended by WHO or the potential ICER threshold in Hong Kong. The cost-effectiveness model will be built using Microsoft Excel or Treeage Pro software.

[Word Count: 4,000]

e) Existing Facilities:

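### The lifetime discounting rule covers costs and QALYs but leaves out life-years, so as written the planned cost per life-year divides discounted costs by undiscounted life-years

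*Combined protocol and SAP*

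**What the plan says.** The economic evaluation is described in the combined protocol and SAP, section d)(iv), under Cost-effectiveness analysis. It runs "over a time horizon of one year (within trial period) and lifetime".

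- **Within-trial analysis.** It "will be evaluated using total costs, the number of tobacco abstinence and total QALYs over the study period".
- **Lifetime analysis.** It uses "Markov modelling that will simulate the annual health status progression of subjects in either intervention or control group", with transitions through disease states to death.
- **Discounting.** "Discounting will only be applied to total costs and QALY calculation under the lifetime horizon". No rate is given.
- **Ratios to be reported.** The same section lists "cost per an additional tobacco abstinence gained, life-years gained, or QALYs gained for the intervention group". The Outcomes paragraph of section d)(ii) also names "the ICER in terms of cost per life-years gain or quality-adjusted life-years gained for intervention versus control group".
- **Decision rule.** The intervention counts as cost-"effective if its ICER will be less than 3 times per capita gross domestic product in Hong Kong recommended by WHO", or below a potential Hong Kong threshold. The rule does not say which ratio is meant.
- **Hypothesis.** The third hypothesis in section c) is that the intervention is "a more cost-effective option for tobacco abstinence and prolonged survival when compared to the control group".

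**The concern.** Life-years and QALYs are named as separate effect measures, each with its own ratio, in both places where the ratios are defined. The discounting sentence names one of them and not the other. An analyst who follows it literally will discount the cost stream and the QALY stream of the Markov model and leave the life-year stream undiscounted.

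The resulting cost per life-year would not be comparable with the cost per QALY from the same model. When the intervention costs more than control, it would also be too low. Because the decision rule is not confined to the QALY ratio, a cost per life-year that is too low could be set against the threshold and used to call the intervention cost-effective.

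The planned sensitivity analysis would not reveal this. It takes its bounds from 95% confidence intervals of estimates, and a discount rate has no confidence interval.

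**Working it through.** The plan gives no discount rate, life-year gain or ratio, so there is no figure of its own to reproduce.

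**Step 1: which model produces life-years.** The within-trial effects are abstinence and QALYs only. Life-years are therefore an output of the lifetime Markov model, where costs are discounted.

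**Step 2: direction.** Let ΔC be the discounted incremental cost, g(t) the life-years gained in year t, and r the annual rate.

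- As written: ICER = ΔC / Σ g(t)
- Consistent: ICER = ΔC / Σ [g(t) / (1+r)^t]

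With r > 0 and g(t) not negative in any year, the second denominator is smaller. For ΔC > 0 the ratio as written is therefore the lower of the two. If ΔC < 0 and life-years are gained, the intervention dominates under both formulas.

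**Step 3: size for a gain at a single time.** If the gain falls at year t, an undiscounted life-year counts (1+r)^t times its discounted value, and the ratio is understated by 1 − 1/(1+r)^t. The rates and times are assumptions.

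| Rate | Year 20: factor | Year 20: understated by | Year 30: factor | Year 30: understated by |
|---|---|---|---|---|
| 1.5% | 1.015^20 = 1.35 | 26% | 1.015^30 = 1.56 | 36% |
| 3% | 1.03^20 = 1.81 | 45% | 1.03^30 = 2.43 | 59% |
| 5% | 1.05^20 = 2.65 | 62% | 1.05^30 = 4.32 | 77% |

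**Step 4: size for a gain spread over time.** Real gains are spread over many years, so a simple annual survival model was run as a cross-check. All of its inputs are assumptions: Gompertz mortality with hazard 0.00003 × exp(0.095 × age), multiplied by 2.0 for continuing smokers and 1.4 for quitters, followed to age 110. The factor is undiscounted divided by discounted life-years gained per quitter.

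| Rate | Entry age 45: life-years gained | Factor at 45 | Factor over entry ages 35 to 55 |
|---|---|---|---|
| 0% | 3.36 | 1 | 1 |
| 1.5% | 2.13 | 3.36/2.13 = 1.6 | 1.4 to 1.8 |
| 3% | 1.40 | 3.36/1.40 = 2.4 | 1.9 to 3.1 |
| 5% | 0.83 | 3.36/0.83 = 4.0 | 2.9 to 6.0 |

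The two approaches agree on direction and on the order of size. Younger entry gives larger factors because the gain falls later.

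**The case against.** **The word *only* may limit the horizon, not the measures.** The section is built on two horizons, and the sentence can be read as saying that nothing is discounted over the one-year trial, which is reasonable. This reading is plausible, and a reader should not infer a deliberate decision to leave life-years undiscounted. It does not close the gap: life-years are missing from the list on either reading, and nothing elsewhere in the supplied text adds them.

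**The appendix on the Markov model is not in the supplied text.** Appendix 8 might specify how outputs are discounted. That limits how firmly one can say what the analysts would do. It does not change what the rule in the main text says.

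**The intervention may be cost-saving.** The plan allows for this. If it saves cost and gains life-years, the conclusion is the same with or without discounting. A reader might infer that the ratio always flatters the intervention; that holds only for a positive incremental cost.

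**The survival hypothesis does not rest on this ratio alone.** Section c) speaks of survival without naming a measure, and QALYs from a model that ends in death also carry survival. This stands: one ratio among three is affected.

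**Undiscounted life-years are a legitimate quantity.** As a labelled secondary result, yes. The plan gives no reason for discounting one health effect and not another from the same model in its reported ratios.

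**Conclusion.** The point holds as an internal inconsistency in a stated rule. As written, the cost per life-year would combine discounted costs with undiscounted life-years, and it would be understated if incremental cost is positive and the discount rate is above zero.

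The size cannot be settled from the documents, which give no rate, no expected age at entry beyond the minimum of 18 years, and no timing of the gain. On the assumed range of 20 to 30 years, the over-weighting is about 1.3 to 1.6 times at 1.5%, 1.8 to 2.4 times at 3% and 2.7 to 4.3 times at 5%. A reader might infer a much larger distortion, for example about sevenfold (1.05^40 = 7.04). That needs a 5% rate and the whole gain placed 40 years ahead, and the documents support neither.

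The primary outcome, the other clinical analyses, and the cost per abstinence and per QALY are not affected. The change should be made because it is simple and because the decision rule leaves the life-year ratio open to comparison with the threshold.

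**What to change.** In section d)(iv), Cost-effectiveness analysis, replace the discounting sentence with:

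> Under the lifetime horizon, costs, life-years and QALYs will all be discounted at the same prespecified annual rate (to be stated); the rate will be varied, including 0%, in sensitivity analysis.

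The sponsor must fill in the rate before the analysis. The 0% run still shows undiscounted life-years, set against undiscounted costs.

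The cost is one sentence of text and a few extra model runs; no new data are needed. The drawback for the sponsor is that, with a positive incremental cost, the cost per life-year will be less favourable than under the present rule.

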- Able to communicate in Cantonese/Mandarin and read Chinese
- Have a smart phone with local network connection

Exclusion criteria:

- Have unstable physical or psychological conditions as advised by doctors or counsellor in charge
- Have become pregnant in the past 2 months

The fourth criterion will be used because our proposed RCT will target the quitters who have recently quit, and exclude those who will have maintained a longer period of abstinence. Our pilot RCT showed that 10 participants on average could be recruited in 8 clinics each week[16]. Our proposed RCT with 30 clinics of the 3 major service providers of smoking cessation, and recruiting quitters who have quit for 7 to 30 days will recruit 25 to 35 participants each week.

Sample size calculation

Our pilot RCT showed that the OR of the CO validated quit rates between the intervention and

control group was 2.04 (95%CI 0.74-5.65) (Intervention: 26.0%, Control: 15.0%)[16]. Because our proposed RCT will recruit quitters who have recently quit, we have conservatively estimated that the OR will be 1.70 (23.0% vs 15.0%). To detect a significant difference of quit rate with 2-tailed z-test by *GPower 3.1* between the two groups with a power of 90% (to reduce type II error) and 5% significant level (type I error), we will need 1,008 participants in total (504 participants per group).

(ii) Methods

Design

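### Cost-effectiveness uncertainty is examined only by setting parameters at their 95% bounds, and the ICER threshold rule read literally would accept a costlier, less effective result

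*Combined protocol and SAP*

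**What the plan says.** The economic plan is in section d)(iv), under Cost-effectiveness analysis.

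- **Within-trial comparison.** It "will be evaluated using total costs, the number of tobacco abstinence and total QALYs over the study period". For the QALYs, "EQ-5D-5L utility data at baseline and follow-ups from trial will estimate QALYs in two groups using area under the curve technique".
- **Lifetime comparison.** A Markov model, described in Appendix 8, which is not in the supplied text.
- **Reported measure.** "The incremental cost-effectiveness ratio (ICER) in terms of cost per an additional tobacco abstinence gained, life-years gained, or QALYs gained".
- **Uncertainty.** One sentence: "Sensitivity analyses will be conducted where each parameter will be set at plausible lower and upper bounds based on 95% confidence interval" of the estimates.
- **Decision rule.** The intervention counts as cost-"effective if its ICER will be less than 3 times per capita gross domestic product in Hong Kong", or below a potential local threshold. Neither threshold is given in figures.

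Section c) makes this one of three hypotheses: "The third hypothesis is that the WhatsApp intervention for a recent quitter is a more cost-effective option for tobacco abstinence and prolonged survival", compared with control. The document mentions no bootstrap, probabilistic sensitivity analysis, interval for the ICER, net benefit or acceptability curve. It gives no rule for a negative ratio, although the same section allows that the intervention may be cost-saving.

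**The concern.** Setting parameters at their bounds shows which inputs move the answer. It does not show how likely the conclusion is to be wrong once costs and effects vary together. Moving all parameters to their bounds at the same time would not supply that probability either.

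The second difficulty is the ratio. An ICER jumps from large positive to large negative as the effect difference passes through zero. A negative value can mean cheaper and better, or dearer and worse. A rule that asks only whether the ICER is below a positive threshold treats the two alike. If the interval for the effect difference includes zero, ICERs calculated at its two limits do not bracket the point estimate, and the limit that is bad for the intervention passes the rule.

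At stake is the economic conclusion, which the plan intends for policymakers.

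**Working it through.** **The plan's own figure.** The documents state nothing numerical about ICER uncertainty. The nearest figure is the sample size (section d)(i)): 23.0% vs 15.0%, two-sided 5%, power 90%.

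n per arm = [1.96 × √(2 × 0.19 × 0.81) + 1.2816 × √(0.23 × 0.77 + 0.15 × 0.85)]² / 0.08² = 503.3, so 504 per arm and 1,008 in total. This reproduces.

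**Incremental cost, from section f).** The documents give no cost per participant, so I use a range built from the budget.
- Moderators only: 89,595 / 504 = HK$178.
- Moderators, nurse and phones: (89,595 + 26,061 + 3,000) / 504 = 118,656 / 504 = HK$235.

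**Cost per extra abstainer at the design rates.** SE of the risk difference = √[(0.23 × 0.77 + 0.15 × 0.85) / 504] = 0.0246. The difference is 0.080, 95% CI 0.032 to 0.128.
- At HK$178: 178 / 0.080 = HK$2,222. At the upper and lower limits of the effect it is HK$1,387 and HK$5,587.
- At HK$235: HK$2,943, with HK$1,837 and HK$7,400.

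These ratios are finite and in order, so there is no breakdown here.

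**Within-trial QALYs.** Assumptions, none of them in the documents: utility gain per quitter over the year of 0.02, 0.05 or 0.10; SD of one-year QALYs of 0.05, 0.10, 0.15 or 0.20. Then QALY difference = 0.08 × gain, and SE = SD × √(2/504) = SD × 0.0630. Clustering by WhatsApp group is ignored; positive correlation would widen the intervals. The 95% intervals are:

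| Gain (difference) | SD 0.05 | SD 0.10 | SD 0.15 | SD 0.20 |
|---|---|---|---|---|
| 0.02 (0.0016) | -0.0046 to 0.0078 | -0.0107 to 0.0139 | -0.0169 to 0.0201 | -0.0231 to 0.0263 |
| 0.05 (0.0040) | -0.0022 to 0.0102 | -0.0083 to 0.0163 | -0.0145 to 0.0225 | -0.0207 to 0.0287 |
| 0.10 (0.0080) | 0.0018 to 0.0142 | -0.0043 to 0.0203 | -0.0105 to 0.0265 | -0.0167 to 0.0327 |

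Eleven of the 12 include zero. To exclude it, the SD would have to be below about 0.013, 0.032 or 0.065 for the three gains.

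**One example.** Difference 0.004, SE 0.0054 (SD = 0.0054 / 0.0630 = 0.086). The 95% limits are 0.004 ± 1.96 × 0.0054 = -0.0066 to 0.0146.

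| Incremental cost | ICER at point estimate | At lower QALY limit | At upper QALY limit |
|---|---|---|---|
| HK$178 | 44,400 | -27,000 | 12,200 |
| HK$235 | 58,900 | -35,800 | 16,100 |

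Both limits give ratios below the point estimate. With a normal distribution around the estimate, the chance of a negative QALY difference is Φ(-0.004/0.0054) = 23%. If the gain were 0.001 with the same SE, it would be Φ(-0.001/0.0054) = 43%.

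**What the literal rule does.** One million independent normal draws of cost and QALYs: mean cost HK$178, cost SE assumed to be 20% of the mean, QALY difference 0.004, SD 0.10. The thresholds are assumed, because the documents give no figure.

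| Threshold per QALY | ICER below threshold | Net benefit above zero |
|---|---|---|
| HK$50,000 | 79% | 53% |
| HK$350,000 | 97% | 71% |
| HK$1,000,000 | 99% | 73% |

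The gap is about 26 points in each row. It equals the share of draws in which the intervention costs more and yields fewer QALYs.

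**The case against.** **The plan is a word-limited proposal, and Appendix 8 may say more.** The appendix is cited for the Markov model, not for sensitivity analysis. The supplied text states one method and one decision rule, and both can be judged as they stand.

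**The illustration rests on assumed inputs.** This stands. The utility gain, QALY SD, cost SE and thresholds are mine. The HK$235 charges the whole nurse budget to the intervention arm, although that line also covers the booklet given to everyone and training of recruitment staff. Both cost figures leave out the control text messages, the full-time assistant's moderating time and any healthcare costs. The sign of the QALY difference does not depend on the cost figure.

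**One at a time is an inference.** This is fair. It is the natural reading of the sentence, not its literal wording, and the text does not say which parameters are varied. In the Markov model the QALY difference is an output, not an input to be set.

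A reader might infer three stronger points that the documents do not support:

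- *That the trial holds participant-level costs whose correlation with effect is being discarded.* The plan speaks only of total costs from the provider perspective and describes no individual resource-use collection. Costs may be assigned by arm or group.
- *That a table of bounds would hide the problem.* It would print the negative ratio. What it would lack is the probability and the joint variation.
- *That the third hypothesis would be left with no error statement at all.* The bounds come from 95% confidence intervals, and the hypothesis names abstinence and prolonged survival, not within-trial QALYs.

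**Conclusion.** The point holds for the economic analysis. The stated method yields no joint uncertainty, no interval for the cost-effectiveness result and no probability of cost-effectiveness. The decision rule, taken literally, does not screen out a costlier, less effective result.

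The sign problem is likely for within-trial QALYs: 11 of 12 assumed combinations, and a 23% chance of a negative difference in the example. The size is illustrative and depends on assumptions that the documents neither confirm nor exclude.

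It would be wrong to extend the sign problem to every ICER. Cost per abstainer stays finite and ordered at the design rates. It would fail only if the observed interval included no effect, as the pilot's did (OR 0.74 to 5.65). For lifetime outcomes the behaviour depends on model inputs not given. The primary abstinence analysis is not touched.

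**What to change.** 1. **Within trial:** bootstrap participants' outcomes together with their costs, using individual costs if they are collected and the assigned costs otherwise. Resample whole WhatsApp groups in the intervention arm and individuals in control, since the statistical analysis section already expects correlated outcomes within groups.
2. **Reporting:** give incremental net benefit (threshold × QALY difference − cost difference) with a 95% interval, and an acceptability curve across the candidate thresholds.
3. **Decision rule:** base the conclusion on net benefit instead of on the ICER being below the threshold, so that dominated results are not accepted.
4. **Lifetime model:** add a probabilistic sensitivity analysis with a distribution for each uncertain parameter. Keep the table of bounds as a supplement, and state which parameters it varies and whether singly.

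The cost is a few days of analyst time. The TreeAge licence is already budgeted, the team includes a co-applicant experienced in cost-effectiveness analysis, and no further participants are needed.

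### The cost-effectiveness rule gives the wrong verdict when the intervention arm does worse, does not exclude cost per abstinence, and leaves two thresholds open

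*Combined protocol and SAP*

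**What the plan says.** Section d)(iv), Cost-effectiveness analysis, plans ICERs in three units: "cost per an additional tobacco abstinence gained, life-years gained, or QALYs gained for the intervention group". They are to be assessed "over a time horizon of one year (within trial period) and lifetime", from the healthcare provider's perspective. One sentence then gives the decision rule. The intervention is cost-"effective if its ICER will be less than 3 times per capita gross domestic product in Hong Kong", and the sentence continues: "recommended by WHO or the potential ICER threshold in Hong Kong". It does not say which of the three ICERs is judged, over which horizon, or which threshold takes precedence. It gives no amount or year for either threshold and sets no condition on the sign of the cost or effect difference.

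No other criterion is offered for the third hypothesis in section c), which expects the intervention to be a "more cost-effective option for tobacco abstinence and prolonged survival when compared to the control group". Uncertainty is handled by sensitivity analyses in which "each parameter will be set at plausible lower and upper bounds based on 95% confidence interval". No interval for the ICER, net-benefit analysis or probabilistic analysis is planned.

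**The concern.** A ratio of two differences loses their signs, so a comparison with a threshold is safe only when the effect difference is known to be positive. The rule lacks that condition. It could therefore endorse an intervention that costs more and helps less.

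The rule also sets one money ceiling against three different units. The plan's own Markov model turns abstinence into life-years and QALYs through disease transitions and relapse. The worth of one abstinence thus depends on how much survival and quality of life it yields, and a GDP multiple does not price it directly. Since section c) names abstinence in the hypothesis, a reader can fairly apply the rule to cost per abstinence, where it discriminates very little.

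Finally, meeting either of two thresholds is enough. What is at stake is the economic conclusion of the trial, which section g) presents as one of its main contributions.

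**Working it through.** **The plan's own figures.** The documents state no ICER, GDP value or threshold amount, so there is none to reproduce. The arm size used below does reproduce. For 23% versus 15%, two-sided 5% and 90% power, n = [1.960 × √(2 × 0.19 × 0.81) + 1.2816 × √(0.23 × 0.77 + 0.15 × 0.85)]² / 0.08² = 503.3, so 504 per arm.

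**Step 1: what the rule does to signs.** Let ΔC be the cost difference, ΔE the effect difference, λ the threshold, and net monetary benefit NMB = λΔE − ΔC.
- If ΔE > 0, then ΔC/ΔE < λ is the same as NMB > 0. The rule is right.
- If ΔE < 0, multiplying by ΔE reverses the inequality, so ΔC/ΔE < λ is the same as NMB < 0. The rule is exactly backwards. This covers the costlier, less effective arm (negative ICER) and the cheaper, less effective arm (positive ICER).

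Example of the first case: ΔC = HK$178 (derived in step 2) and abstinence 2 points lower give 178/(−0.02), about −HK$8,900, which is below any positive threshold.

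**Step 2: rough delivery cost per intervention participant** (section f), read as Hong Kong dollars).
- Moderators only: 1,991 × 5 × 9 = 89,595; 89,595/504 = about HK$178.
- Adding the whole nurse line (1,241 × 21 = 26,061) and phones (3,000): 118,656/504 = about HK$235.
- Extreme case, the whole grant charged to the intervention: 967,620/504 = about HK$1,920.

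**Step 3: cost per extra quitter at the design difference of 8 points.** 178/0.08 = about HK$2,200; 235/0.08 = about HK$2,900; 1,920/0.08 = about HK$24,000.

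**Step 4: smallest difference that passes.** Assume GDP per capita of HK$100,000 to 400,000, so λ runs from 300,000 to 1,200,000. At HK$235 the break-even risk difference is 235/300,000 = 0.078 points, down to 235/1,200,000 = 0.020 points. With 504 per arm and missing outcomes counted as smoking, the smallest non-zero difference is 1/504 = 0.2 points. Every positive difference therefore passes, and by step 1 so does every negative one. Only an exact tie does not.

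With the whole grant charged, one extra quitter costs HK$967,620 and passes only if GDP per capita exceeds 967,620/3 = about HK$322,500. The statement that every difference passes therefore belongs to the HK$178 to 235 range.

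**Step 5: how often the rule passes on abstinence.** Simulation with 504 per arm and 400,000 draws; total cost difference fixed at HK$89,595 or HK$121,156 (moderators, nurse, phones and phone service); λ of 300,000, 600,000 and 1,200,000. Results were the same across these settings.

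| True rates | Rule as written | With ΔE > 0 also required |
|---|---|---|
| 15% v 15% | 96.6% | 48.2% |
| 12% v 15% | 98.6% | 7.5% |
| 23% v 15% | about 100% | 99.9% |

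**Step 6: one-year QALYs.** With the same costs and thresholds, an assumed QALY standard deviation of 0.05 to 0.20 and no true effect, the rule as written passes 90% to 99.5% of the time. Requiring a gain lowers this to 40% to 50%. A point-estimate rule therefore still passes about half the time under no effect, even with the signs handled correctly.

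**The case against.** The best defence is that the section speaks of cost per unit gained, so the rule presupposes a gain and is not engaged when the intervention arm does worse. The section also mentions a cost-saving result separately, and a health economist would normally report dominance. This is a plausible account of intent, and the documents do not show that the authors would call a dominated arm cost-effective. But the condition is not written into the rule.

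Second, the Outcomes part of section d)(ii) lists the abstinence ICER apart from the life-year and QALY ICERs, so the threshold may be meant only for the latter. That is possible. The rule does not say so, and section c) puts abstinence inside the hypothesis. A low cost per quitter also partly reflects a cheap intervention, not only a weak rule.

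Third, the cost figures are partial, and this stands. The nurse also designs the booklet that both arms receive and trains and meets recruitment staff. The full-time research assistant's moderating time is left out, control-arm messaging is not subtracted, and other provider healthcare costs are absent. These could change the size or even the sign of the cost difference. The sign argument in step 1 does not depend on them.

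Fourth, later use of the laxer threshold is a possibility that the wording allows, not something the plan announces.

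**Conclusion.** The concern holds for the rule as worded. It reverses whenever the effect difference is negative, it does not keep a GDP multiple away from cost per abstinence, and it lets either of two unquantified thresholds suffice. The first fault is algebra and needs no assumption. The claim that every non-zero abstinence difference passes rests on a positive cost difference of HK$178 to 235, 504 per arm, and an assumed GDP per capita of HK$100,000 to 400,000. The QALY pass rates rest on assumed standard deviations and a fixed cost difference.

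A reader might infer that the rule cannot decide the third hypothesis at all. The documents do not support that. For life-years or QALYs with cost and effect differences both positive, comparison with a threshold is a usable criterion once the threshold and horizon are named. The primary abstinence comparison and the sample size are not touched.

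**What to change.** Replace the rule with: the intervention is considered cost-effective if the incremental net monetary benefit (threshold × QALY difference − cost difference) is above zero. In addition:
- Before unblinding, name the deciding horizon and fix one threshold with its amount and year. Show the other threshold as a sensitivity analysis.
- Report the probability that net benefit is positive, by bootstrap or probabilistic sensitivity analysis.
- Report cost per abstinence and per life-year with dominance stated where it occurs, and set no GDP threshold on cost per abstinence.
- Align the third hypothesis in section c) with the deciding outcome, since it now names abstinence and survival and not QALYs.

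This takes a few sentences and a little more analysis, with no new data collection. The price is that a claim of cost-effectiveness becomes harder to reach.
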